6.2.7. Moderate Exacerbations

A moderate exacerbation is defined as a clinically judged deterioration in asthma control as determined by the investigator and as evidenced by new or worsening asthma signs or symptoms based on the patient history, asthma control diary, physical examination, and/or ambulatory or clinic visit assessment of lung function AND that results in a medical intervention requiring additional asthma controller medication that was not a systemic corticosteroid and did not result in an asthma-specific hospitalization or emergency department visit (ie, medical intervention that did not otherwise meet the criteria for the primary endpoint).

Additional medication that would satisfy the moderate exacerbation definition occurring within 7 days of the last day of a prior event will be considered as part of the same event for analysis purposes. Similarly, additional medication that would satisfy the moderate exacerbation definition occurring within 7 days prior to the start date of another event satisfying the definition of a CAE (or occurring concurrently with a CAE) will be considered part of the CAE event and will not be counted towards the analysis of moderate exacerbations.

The analysis for moderate exacerbations will be similar to the on-treatment analysis described for the primary endpoint (Section 6.2.3). In addition, the analysis of moderate exacerbations will not exclude exacerbation duration from the offset.

6.3. Secondary Efficacy Variable(s) and Analysis

As described previously in Section 4.5, an on-treatment approach will be adopted as the primary analysis for the efficacy variables assessed by-visit. In this analysis, the treatment period will be defined from the first dose of study drug to the end of treatment (week 52) visit for patients who completed treatment and from the first dose of study drug to the last dose of study drug (+4 weeks) for patients who discontinued treatment early. Measurements collected outside of these defined timeframes will be excluded from the analyses and endpoint will be defined within these timeframes. All results will be included in the patient listings. For selected key variables, additional sensitivity analyses may also be performed in which all post-baseline measurements collected during the study will be included and endpoint will be defined within this extended timeframe.

6.3.1. Secondary Variables

The secondary efficacy endpoints are as follows:

- change in pre-bronchodilator FEV₁ from baseline/DoR at week 52
- change in Asthma Quality of Life Questionnaire for patients 12 years and older (AQLQ +12) score from baseline/DoR at week 52
- change in 6-item Asthma Control Questionnaire (ACQ-6) score from baseline/DoR at week 52
- change in total asthma symptom scores (day and night) from baseline at week 52
- percentage of asthma control days from baseline/DoR to week 52
- change in St. George's Respiratory Questionnaire (SGRQ) from baseline/DoR at week 32
- time to first clinical asthma exacerbation during the 52-week treatment period
- frequency of exacerbations requiring hospitalization or emergency department visits per patient during the 52-week treatment period
- frequency of moderate exacerbations defined as exacerbations requiring additional asthma controller medication that was not a systemic corticosteroid and that did not result in an asthma-specific hospitalization or emergency department visit during the 52-week treatment period

Testing of the secondary variables will be performed using the sequential testing procedure in the order as specified above, as described in Section 4.3.

6.3.3. Pulmonary Function Tests

6.3.3.1. Variable Definition

Pulmonary function tests will be measured using spirometry, according to ATS/ERS 2005 procedural guidelines. Pre-bronchodilator assessments (FVC, FEV₁, FEF_{25%-75%}) are measured at weeks 2, 4, 8, 12, 16, 32, and 52 and post-bronchodilator assessments (FEV₁) are measured at weeks 16, 32, and 52.

The FVC is the volume of air, in liters (L), that can be forcibly blown out after full inspiration. The FEV₁ is the volume of air (L) that can be forcibly exhaled from the lungs in the first second. The FEF_{25%-75%} is the forced expiratory flow (L/second) at 25% to 75% forced vital capacity. The percent (%) predicted FEV₁ is derived as the actual FEV₁ divided by the standard predicted FEV₁ (multiplied by 100). The National Health and Nutrition Examination Survey (NHANES) III reference equations will be used. An additional correction factor will be applied for Asian patients ([Hankinson et al 2010](#)).

6.3.3.2. Analysis

Summary statistics of actual values and change from baseline to each scheduled visit will be provided by treatment group.

Analysis of the change from baseline to each scheduled visit will be performed using a mixed effect model for repeated measures (MMRM) including fixed effects for treatment, visit, treatment by visit interaction, age group (12 to <18 years and ≥ 18 years), blood eosinophil counts at enrollment (300 to <400/ μL and $\geq 400/\mu\text{L}$), and sex, height and baseline value as covariates, and patient as a random effect. Age and blood eosinophil categories will be based on data recorded in the clinical database. An unstructured covariance matrix will be used for the within patient correlation modeling. If the fit of the unstructured (UN) covariance matrix fails to converge, the following covariance structures will be tried in order until convergence is reached: first order autoregressive (AR[1]) and compound symmetry (CS). Based on the MMRM model, the treatment effect, the difference from placebo, and the associated 95% CI will be presented together with the corresponding p-value.

The following sample SAS[®] code pertains to the MMRM analysis.

```
proc mixed data=<<>>;
  class patient visit treatment strata1 strata2 sex;
  model change=treatment strata1 strata2 sex height baseline visit treatment*visit
    /ddfm=kr alpha=0.05;
  repeated visit /type=un subject=patient r;
  lsmeans treatment*visit / diff cl;
  ods output lsmeans=<<>>;
  ods output diffs=<<>>;
run;
```

Model results will only be reported if there are at least 15 patients contributing to the analysis in each treatment group; otherwise only the descriptive statistics will be displayed. A line graph presenting the LS mean change from baseline over time (at each visit) will be provided for pre-bronchodilator FEV₁, [REDACTED] by treatment group.

Pre-bronchodilator FEV₁ at Week 52 will additionally be examined for the selected subgroups defined in Section 3.4. The analysis of subgroups will use a MMRM model similar to the one described above. Subgroups will be presented graphically using forest plots.

The proportion of patients achieving an increase of ≥ 100 mL in FEV₁ from baseline to each scheduled visit will be summarized. A stratified (based on randomization strata) Cochran-Mantel-Haenszel (CMH) test will be used to analyze the proportion of patients achieving an increase of ≥ 100 mL in FEV₁ from baseline to Week 52.

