#### **9.5.6.2. Secondary Efficacy Analysis**

All efficacy variables will be summarized by treatment group. For continuous variables, the summary statistics will include n, mean, SD, standard error (SE), median, minimum, and maximum.

Analysis of pulmonary function tests, AQLQ +12, ACQ-6, total asthma symptom scores, and SGRQ use will use the mixed model repeated measures model with treatment group, visit, treatment and visit interaction, baseline value, and stratification factors as fixed effects and patient as a random effect.

Analysis of percentage of asthma control days will use an analysis of variance (ANOVA) model with treatment group and stratification factors.

The Kaplan-Meier (KM) method will be used to estimate and compare the distributions of time to first CAE between treatment groups. Differences will be compared using a log rank test adjusting for the stratification factors.

The frequency of exacerbations requiring hospitalization or emergency department visits and the frequency of moderate exacerbations will be examined separately. The analysis will use similar methodology to that described for the primary analysis.

Additional covariates or factors may be added to the statistical models. These will be detailed in the statistical analysis plan.

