6.3.4.2. Analysis

Summary statistics of actual values and change from baseline to each scheduled visit will be provided by treatment group.

Analysis of the change from baseline to each scheduled visit will use the same MMRM model described in Section 6.3.3.2 with the exception of inclusion of sex and height in the model. A line graph will be provided for the LS mean change from baseline over time (at each visit).

AQLQ +12 at Week 52 will additionally be examined for the selected subgroups defined in Section 3.4. The analysis of subgroups will use a MMRM model similar to the one described above. Subgroups will be presented graphically using forest plots.

The proportion of patients achieving an increase of ≥ 0.5 in the AQLQ +12 score from baseline to each scheduled visit will be summarized. A stratified (based on randomization strata) Cochran-Mantel-Haenszel (CMH) test will be used to analyze the proportion of patients achieving an increase of ≥ 0.5 in the AQLQ +12 score from baseline to Week 52.

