6.3.9.2. Analysis

Compliance with the daily diary assessments will be derived for each patient as an additional measure of protocol adherence. A diary compliant day will be defined as a day with non-missing values for all diary assessments, including AM/PM asthma symptom score, [REDACTED],

[REDACTED]. Diary compliance will be derived as a percentage over the treatment period:

- $\text{Diary compliance (\%)} = 100 \times (\text{total number of diary compliant days} / \text{total number of days during the treatment period})$

The treatment period for diary compliance extends from the first day of study drug to the last day of study drug. Note that, in this analysis, missing data will be treated as non-compliant (eg, if compliance cannot be assessed for a given day due to missing data, then the day will not be counted as a diary compliant day).

[REDACTED]

A weekly average of the daily diary measures ([REDACTED], total asthma symptom score, and [REDACTED]) will be derived (see [Table 3](#) for the definition of analysis days for diary data). The average will be calculated as the sum of all values divided by the number of non-missing assessments. There will be no imputation of missing data. At least 4 of the 7 measurements need to be recorded for a week to be included in the analysis; otherwise the week will be treated as missing.

[REDACTED] and asthma control days will be derived and analyzed as percentages over the relevant analysis period, derived as:

- $\text{Asthma control days (\%)} = 100 \times (\text{total number of asthma control days} / \text{total number of days during the analysis period})$

[REDACTED]

The analysis periods are as defined in [Section 6.3](#). Note that, in this analysis, missing data will be treated as non-responders (eg, if asthma control cannot be assessed for a given day due to missing data, then the day will not be counted as an asthma control day).

Summary statistics of actual values and change from baseline to each week will be provided by treatment group.

Analysis of the change from baseline to each week will use a similar MMRM model as described in [Section 6.3.3.2](#) with the exception of inclusion of sex and height in the model.

Analysis of the percentage of [REDACTED] and percentage of asthma control days will be performed using an analysis of variance (ANOVA) model with fixed effects for treatment, age group, and blood eosinophil counts at enrollment.

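### The MMRM for FEV1, AQLQ +12 and ACQ-6 applies one baseline slope at every visit, which may cost a little precision at week 52

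*SAP*

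**What the plan says.** SAP 6.3.3.2 describes the model for change in lung function as "including fixed effects for treatment, visit, treatment by visit interaction, age group", with eosinophil group, sex, height and baseline value also included. The sample code agrees: "model change=treatment strata1 strata2 sex height baseline visit treatment*visit". Baseline appears once and is not crossed with visit. Protocol 9.5.6.2 has the same structure: "treatment and visit interaction, baseline value, and stratification factors as fixed effects and patient as a random effect".

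On covariance, SAP 6.3.3.2 states: "An unstructured covariance matrix will be used for the within patient correlation modeling". If that fails to converge, AR(1) and then compound symmetry are tried.

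AQLQ +12 (SAP 6.3.4.2) "will use the same MMRM model described in Section 6.3.3.2 with the exception of inclusion of sex and height in the model", and ACQ-6 (6.3.5.2) and SGRQ (6.3.6.2) are handled in the same way. The diary section differs slightly: "Analysis of the change from baseline to each week will use a similar MMRM model". Pre-bronchodilator spirometry measures "are measured at weeks 2, 4, 8, 12, 16, 32, and 52". The tested time point in SAP 6.3.1 is week 52 for FEV1, AQLQ +12 and ACQ-6, and week 32 for SGRQ.

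**The concern.** When change from baseline is regressed on baseline, the slope at a visit depends on how strongly that visit correlates with baseline. If the correlation weakens over 52 weeks, the slope steepens. A single slope must then compromise between visits. Under unstructured covariance it is pulled towards the early visits, where residual variance given baseline is smaller. Four of the seven FEV1 visits fall in the first 12 weeks, but the test is made at week 52. The covariance model lets variances and correlations differ by visit, while the mean model does not let the baseline effect differ.

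What is at stake is precision at the tested visit. Some baseline variance that could be removed stays in the week-52 comparison. FEV1 is the first of nine secondary endpoints in the fixed sequence, so a failure there stops inferential testing of the other eight.

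**Working it through.** **The plan's own figure.** The only power statement concerns the primary CAE rate (above 99% in the protocol synopsis; above 90% in Protocol 9.1 and SAP 2.3). With rates 2.9 and 2.9 × 0.55 = 1.595, dispersion 1.2 and 225 per arm:

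- Var(log RR) = (1/2.9 + 1/1.595 + 2 × 1.2)/225 = 0.01499, so SE = 0.1224.
- |ln 0.55|/SE = 0.5978/0.1224 = 4.88, giving power of 99.8% at two-sided 0.05.

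The figure is reproduced, but it says nothing about the MMRM endpoints, for which no SD, correlation, effect size or power is given.

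**Inputs from the SAP.** Post-baseline visits: 7 for FEV1 (6.3.3.1), 6 for AQLQ +12 (6.3.4.1), 14 for ACQ-6 (6.3.5.1). Total 450 patients, 1:1 (2.3, 2.4).

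**Assumed inputs.** Equal variances (set to 1), complete data, and correlation ρ(gap) = a × exp(−λ × gap in weeks), with λ = ln(a/r52)/52. Here a is the correlation extrapolated to zero gap and r52 the correlation of baseline with week 52.

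**Formulas.**

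- Visit-specific slope of change on baseline: b_j = ρ_j − 1.
- Common slope under unstructured covariance: β = (1′S⁻¹b)/(1′S⁻¹1), with S the residual covariance given baseline.
- Variance ratio at week 52, common slope against visit-specific slopes: VR = 1 + (b_52 − β)²/S_52, with S_52 = 1 − r52².
- Excess SE = √VR − 1. Patient equivalent = 450/VR.

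**Worked case: FEV1, 0.8 falling to 0.6.** b_52 = −0.4 and β = −0.2522; the week-2 slope is −0.2088, so the compromise lies near the early visits. S_52 = 1 − 0.36 = 0.64. VR = 1 + (0.1478)²/0.64 = 1.034. Excess SE is 1.69%, and 450/1.0342 = 435, so about 15 patients.

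**Range of assumptions** (VR, with excess week-52 SE in brackets):

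| a → r52 | FEV1 | AQLQ +12 | ACQ-6 |
|---|---|---|---|
| 0.70 → 0.70 | 1.000 (0%) | 1.000 (0%) | 1.000 (0%) |
| 0.80 → 0.70 | 1.010 (0.51%) | 1.009 (0.44%) | 1.009 (0.46%) |
| 0.80 → 0.60 | 1.034 (1.69%) | 1.029 (1.44%) | 1.032 (1.59%) |
| 0.75 → 0.50 | 1.042 (2.09%) | 1.036 (1.77%) | 1.039 (1.93%) |
| 0.90 → 0.70 | 1.051 (2.53%) | 1.044 (2.18%) | 1.050 (2.48%) |
| 0.85 → 0.50 | 1.096 (4.67%) | 1.080 (3.93%) | 1.093 (4.55%) |
| 0.80 → 0.40 | 1.100 (4.86%) | 1.082 (4.02%) | 1.095 (4.65%) |

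In the 0.8 to 0.6 row the patient equivalents are 435, 437 and 436, a loss of 15, 13 and 14 of 450.

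**Check with dropout.** FEV1 schedule, 450 patients, about 14% missing-at-random dropout, maximum likelihood, 60 runs per scenario. The ratio of model SEs (common slope over visit-specific) was 1.000 with equal slopes, 1.019 for 0.8 to 0.6, and 1.053 for 0.8 to 0.4. Mean treatment estimates from the two models differed by at most 0.002 SD.

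**Endpoints outside the claim.** SGRQ is measured after baseline only at weeks 32 and 52 and tested at week 32; its excess SE is 0% to 0.19% over the same scenarios. The weekly symptom score would need 51 extra terms on top of an unstructured matrix with 52 × 53/2 = 1,378 parameters.

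**The case against.** The strongest reply is that no loss has been found, only assumed. The documents contain no correlations, and with equal slopes the gain is exactly zero. That stands, and it is why the range starts at 0%. The calculation also leaves out the other covariates (sex and height for FEV1, age group and eosinophil group), and the direction of that effect is not shown. If the fit falls back to compound symmetry, visits are weighted more evenly and the loss shrinks: an equal-weight approximation for 0.8 to 0.6 gives VR 1.025, 1.021 and 1.014 for FEV1, AQLQ +12 and ACQ-6.

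A second reply is that the extra terms are not free everywhere. Subgroup models reuse this MMRM and are reported with as few as 15 patients per arm. At that size, 13 more ACQ-6 parameters beside a 14 × 14 unstructured matrix (105 parameters) are not negligible. This stands and limits the fix.

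A reader might infer three stronger things that the documents do not support:

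- **That all five MMRM endpoints are affected alike.** SGRQ is tested at week 32 with two visits and loses almost nothing. For the weekly symptom score it is not established that the single term saves nothing.
- **That the week-52 estimate is biased.** Randomization makes baseline independent of treatment, so with complete data a common slope does not shift the expected contrast. The simulation with dropout showed no material difference between the models.
- **That the SAP departs from the protocol.** Both specify a single baseline term.

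**Conclusion.** The point holds as a cheap, optional improvement in efficiency for the main FEV1, AQLQ +12 and ACQ-6 analyses at week 52. It is not an error in the plan. The excess SE runs from 0% to about 5% over the assumed correlations. A middle case is 1.4% to 1.7% with complete data (13 to 15 of 450 patients), or 1.9% for FEV1 with dropout. The size rests on an assumed decline in correlation with baseline, equal variances over time and unstructured covariance. No secondary power target exists against which to judge the loss.

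**What to change.** Before unblinding, amend SAP 6.3.3.2 to add `baseline*visit` to the model text and sample code for the full-ITT FEV1 analysis, and carry it into 6.3.4.2 and 6.3.5.2. Because several sections inherit the model by reference, state explicitly which analyses take the new term. Subgroup models should keep the single baseline term; SGRQ (6.3.6.2) and the weekly diary score (6.3.9.2) need no change.

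The cost is 6 extra parameters for FEV1, 5 for AQLQ +12 and 13 for ACQ-6, against about 450 patients, with no new data. When the slopes were equal, the FEV1 simulation showed no SE penalty (ratio 1.000). For the other two endpoints, the negligible cost is inferred from the parameter count and was not simulated. Protocol 9.5.6.2 already lets the SAP add covariates or factors, so no protocol amendment is needed. The downside is a slightly larger model with no gain if the slopes turn out equal.

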6.3.4. AQLQ +12

6.3.4.1. Variable Definition

The AQLQ +12 is a modified version of the standardized AQLQ which measures functional impairments experienced by adults ≥ 17 years of age. The AQLQ +12 is valid for patients aged 12-70 years.

The AQLQ +12 is a 32-item instrument administered as a self assessment at weeks 4, 8, 12, 16, 32, and 52. Patients are asked to recall their experiences during the previous 2 weeks and to score each question on a 7-point scale (7 = no impairment, 1 = severe impairment).

The 32 questions (items) in the AQLQ +12 are divided into 4 domains:

- Activity limitations: Items 1-5, 11, 19, 25, 28, 31, 32
- Symptoms: Items 6, 8, 10, 12, 14, 16, 18, 20, 22, 24, 29, 30
- Emotional function: Items 7, 13, 15, 21, 27
- Environmental stimuli: Items 9, 17, 23, 26

6.3.4.1.1. Missing data handling and total score calculation

The overall and domain scores of the AQLQ +12 are derived as the average of the corresponding items; the analysis will be based on the available data.

For incomplete data, the overall AQLQ +12 score for a particular visit will not be calculated if 3 or more responses are missing with no more than 1 per domain. For the symptom and activity domain total scores, calculation will require no more than 1 missing item. Total scores for the other 2 domains will be regarded as missing if 1 or more item is missing.

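### As worded, the AQLQ +12 rule withholds the overall score only for 3 or 4 missing items in different domains, and scores forms that lack a whole domain

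*SAP*

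**What the plan says.** SAP 6.3.4.1 describes the instrument: "The AQLQ +12 is a 32-item instrument administered as a self assessment at weeks 4, 8, 12, 16, 32, and 52". It assigns the items to four domains. The largest is symptoms, with 12 items; next comes activity, with 11 ("Activity limitations: Items 1-5, 11, 19, 25, 28, 31, 32"). The emotional domain has 5 items, and the smallest, the environmental domain, has 4 ("Environmental stimuli: Items 9, 17, 23, 26").

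SAP 6.3.4.1.1 then says how scores are formed. The overall and domain scores are "derived as the average of the corresponding items; the analysis will be based on the available data". For incomplete forms, the overall score at a visit "will not be calculated if 3 or more responses are missing with no more than 1 per domain". The same section scores the symptom and activity domains only if at most one item is missing, and the emotional and environmental domains only if none is.

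SAP 6.3.1 lists "change in Asthma Quality of Life Questionnaire for patients 12 years and older (AQLQ +12) score from baseline/DoR at week 52" second among the secondary endpoints, which are tested in the listed order after the primary (SAP 4.3).

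**The concern.** A limit of one missing item per domain is a natural condition for allowing a score. Here it is joined to the condition for refusing one, so it narrows the set of forms that are refused. Among forms with 3 or more missing items, the rule refuses those whose gaps are spread thinly and accepts those whose gaps are concentrated in a domain.

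If it is programmed as written, an overall score could be the mean of a form with one domain entirely absent, which does not measure the same thing as a score over all four domains. That score enters the repeated-measures model for the third test in the fixed sequence, the subgroup analyses at week 52 and the Cochran-Mantel-Haenszel test of a gain of at least 0.5 (SAP 6.3.4.2). A p-value above 0.05 at this step ends inferential testing for every later secondary endpoint.

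**Working it through.** **Inputs.** Domain sizes, counted from the item lists in SAP 6.3.4.1: activity 11, symptoms 12, emotional 5, environmental 4. Sum: 11 + 12 + 5 + 4 = 32, with items 1 to 32 each appearing once. This reproduces the plan's own figure of 32 items.

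**The rule as logic.** Let M be the total number of missing items and m the largest number missing in any one domain. As written, the score is withheld if M ≥ 3 and m ≤ 1. Otherwise the score is the mean of the available items.

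**Which forms are withheld.** With four domains, m ≤ 1 implies M ≤ 4. So the score is withheld only in two cases:

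- M = 3, in three different domains: 11×12×5 + 11×12×4 + 11×5×4 + 12×5×4 = 660 + 528 + 220 + 240 = 1,648 of the 4,960 three-item patterns.
- M = 4, one in each domain: 11×12×5×4 = 2,640 of the 35,960 four-item patterns.

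The total is 1,648 + 2,640 = 4,288 patterns. For M ≥ 5, some domain must lack at least 2 items, so m ≥ 2 and the score is never withheld, even with 31 of 32 items missing. These counts show the logic only; they are not expected frequencies.

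**Literal rule against three plausible intentions.** A: fewer than 3 missing and at most 1 per domain. B: at most 3 missing and at most 1 per domain. C: fewer than 3 missing, with no domain limit.

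| Missing items | Share of 32 | As written | A | B | C |
|---|---|---|---|---|---|
| 1, or 2 in different domains | 3%, 6% | scored | scored | scored | scored |
| 2 in one domain | 6% | scored | not | not | scored |
| 3 in three domains | 9% | not | not | scored | not |
| 3 in one domain | 9% | scored | not | not | not |
| all environmental (4) | 12.5% | scored | not | not | not |
| all emotional (5) | 16% | scored | not | not | not |
| all activity (11) | 34% | scored | not | not | not |
| all symptoms (12) | 37.5% | scored | not | not | not |

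All three intentions refuse a form with a whole domain missing; the written rule accepts it. The intentions disagree with each other on 2 missing in one domain and on 3 missing in three domains.

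**Is it repaired elsewhere?** Protocol 6.4 has no rule for missing items. SAP 4.4 says only that observed data are used for variables other than the primary. The SAP preface gives the SAP precedence over the protocol. The domain rules in 6.3.4.1.1 point the other way: a form with no activity items gets no activity score, yet it gets an overall score.

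**The case against.** The best defence is that nobody would program the sentence literally. The domain rules beside it are strict, and a careful programmer would query the wording rather than average a form with an empty domain. That may well happen, but the text does not say what the answer to the query should be. Intentions A, B and C are all reasonable and give different scores for some forms. The choice belongs in the SAP, made blind.

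A second objection is that the harm is easily overstated, and this stands. A reader might infer that the rule is reversed for incomplete forms in general, or that nearly complete forms are lost. The documents do not support that: every form with 1 or 2 missing items is scored as the text stands. Nor is refusing a form with 3 spread-out missing items clearly an error, since intentions A and C refuse it too. What is clearly wrong is the acceptance of forms with 3 or more missing items when at least 2 of them fall in one domain.

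A third objection also stands: the documents report no item-level missingness, and nothing indicates that it would differ between the arms. No bias in the AQLQ +12 comparison has been shown.

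**Conclusion.** The rule is wrong as written. For forms with 3 or more missing items, it withholds the overall score in exactly two situations (3 or 4 missing, each in a different domain) and allows it in all others, including when a full domain is absent. It also conflicts with the domain rules in its own section, and nothing else in either document corrects it.

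The endpoint is confirmatory, so the rule should be unambiguous, but the point is minor. The numerical effect cannot be calculated without a rate of missing items. That it is probably small is a judgement, not a result from the documents. It would be tempting to conclude that the AQLQ +12 test is compromised; the documents do not support that, because they do not show that forms with large gaps occur. The conclusion rests on a literal reading of one complete sentence and on the domain lists in SAP 6.3.4.1.

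**What to change.** Before unblinding, replace the sentence in SAP 6.3.4.1.1 with one that joins the two limits by *or*: the overall score for a visit is set to missing when at least 3 of the 32 responses are absent, or when any single domain lacks more than 1. The sponsor should first confirm both limits against the instrument's scoring instructions, because the documents do not settle them.

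The drafting cost is one sentence. There is also a cost in data. Forms with 2 missing items in one domain, which the current text scores, would become missing: C(11,2) + C(12,2) + C(5,2) + C(4,2) = 55 + 66 + 10 + 6 = 137 of the 496 two-item patterns. Forms with 3 missing items in three domains would remain unscored, unless the sponsor confirms that up to 3 missing items are allowed (intention B).
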